## 12.5 Secondary Analysis

Secondary outcomes include physical symptom assessment, mood symptoms (measured through a subscale of PROMIS-29), spiritual distress assessment, mortality, and assessment of caregiver burden by the linear mixed model.

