## 12.1 Statistical Design

Differences in primary and secondary outcomes between intervention and control arms will be evaluated at each individual time point as well as across the intervention period.

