### 12.1.1 Randomization

Randomization occurs immediately after enrollment. Participants are stratified by study site. Using the REDCap database, group assignment (intervention or control) is determined via a computer-generated random allocation with a block size of 6. Patients, caregivers, and surgeons cannot be blinded to group assignment due to practical considerations; however, the principal investigator and analysis team are blinded to participant randomization. The research team collecting outcome data are blinded to participant randomization, whenever possible.

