### 12.5.1 Analysis Population

Our study will use an intent-to-treat approach in which all data from study patients in both intervention and control arms are used, regardless of the level of adherence to the study arm.

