### 12.5.2 Analysis Plan

Depending on the format of the variable, the effect of group assignment (intervention or control) on the secondary outcomes will be tested at each visit with two-sample t-test/Mann-Whitney test or Fisher's exact test/chi-squared test. The effect of intervention on secondary variables after accounting for various confounding variables will be determined using a linear mixed model that accounts for within-subject variations due to repeated measures. For end-point secondary outcomes, Kaplan-Meier method or Cox proportional hazards models will be used.

The overall level of statistical significance was set at  $p<0.05$ . For all models, the research team will identify possible confounding variables for model adjustment, including baseline attributes. Using peer-reviewed literature, the research team has identified confounding variables that models will be adjusted for. These covariates include patient gender, age, race, education, and health status.

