### **12.6.3 Effect size justification**

The means, standard deviations, and effect sizes were based on previous research  supporting that patients receiving medical oncologist-palliative care co-management had better quality of life (measured by Functional Assessment of Cancer Therapy – Lung; FACT-L) than patients receiving medical oncologist alone management. Mean score differences in FACT-L were  $98.0 \pm 16.7$  ( $n = 74$ ) in the intervention group and  $91.5 \pm 16.5$  ( $n = 77$ ) in the control group resulting in an effect size of 0.42 (unpaired two-sample t-test). Since the FACIT-Pal scale used in this study is a direct corollary of the FACT-L scale, this effect size was used to estimate the sample size for the present study. The sample size and power of this study are based on the quality of life measure, FACIT-Pal. Based on the unpaired two-sample t-test, the present study was powered to detect an anticipated small-to-moderate effect size of 0.4 at 12 weeks with 90% power and probability type I error of 0.05 (two-sided). Patients will be nested within the four intervention sites, which will introduce some within-site correlation that could decrease the efficiency of these estimators. Thus, a variance inflation factor of 20% was incorporated in the sample size estimation. Additionally, it is predicted that this study will have missing data due to patients discontinuing participation in the study and death. Based both on the research team's past experiences conducting studies in this population and already published perioperative mortality data, we assumed a dropout rate of 11% and a mortality rate at 12 weeks of 3%; thus, patient completion rate was estimated to be 0.86. Together, with the assumptions outlined here, the estimated sample size needed for the present study is a total of 186 patients per arm (372 patients total) and our goal was to recruit 380 patients.

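### Sections 12.5 and 12.5.2 should be reconciled on mortality, and the hospitalization/ER count and the yes/no outcomes need a suitable adjusted model

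*Combined protocol and SAP*

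**What the plan says.** Section 12.5 is a single sentence. It lists physical symptoms, mood, spiritual distress, mortality and caregiver burden, and closes with "mortality, and assessment of caregiver burden by the linear mixed model". It does not mention health care utilization, advance care planning or prognostic awareness.

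Section 12.5.2 has three layers:

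- **Unadjusted, by visit:** a t-test or Mann-Whitney test, or Fisher's exact or chi-squared test, according to the format of the variable.
- **Adjusted:** "The effect of intervention on secondary variables after accounting for various confounding variables will be determined using a linear mixed model", described as accounting for repeated measures within a subject. No outcome is excepted.
- **Survival methods:** "For end-point secondary outcomes, Kaplan-Meier method or Cox proportional hazards models will be used". Which outcomes these are is not stated, nor are the time origin and the censoring date.

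The same section applies adjustment to all models: "These covariates include patient gender, age, race, education, and health status".

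Section 10.2.2 defines utilization as a number of hospitalizations and/or ER visits after surgery. The outcome table there also lists presence of advance care planning and mortality. In the Study Calendar (Section 9), medical abstraction is marked once, at Off Study, and advance care planning is marked at Pre-Study and at 6 months.

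**The concern.** A linear mixed model for repeated measures suits scale scores collected at several visits. It does not suit a death that happens once, a skewed count of admissions, or a yes/no item. Read literally, the plan gives that model to all three, with a survival option for outcomes left unnamed. The closing phrase of Section 12.5 may attach only to caregiver burden, but the grammar does not settle it.

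At stake is whether each secondary outcome has a valid, prespecified adjusted analysis. As written, an analyst who needs an adjusted result for utilization or advance care planning must either fit an ill-suited model or choose a different one after the fact.

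**Working it through.** **1. Outcomes against the adjusted models named in 12.5.2**

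| Outcome | Type | Adjusted model named |
|---|---|---|
| ESAS, PROMIS-29, FACIT-Sp-12, ZBI-12 | repeated scale scores | linear mixed model: suitable |
| Mortality | one event per patient | Cox, if mortality is an end-point outcome; linear mixed model, on one reading of 12.5 |
| Hospitalizations/ER visits | count | linear mixed model only |
| Presence of advance care planning | yes/no by its wording | linear mixed model only |
| Prognostic awareness | response format not given | linear mixed model only |

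No Poisson, negative binomial, logistic or generalized mixed model appears in the document. Kaplan-Meier gives no covariate-adjusted effect, so only Cox could supply one for mortality.

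**2. The design figure is untouched.** Section 12.6.2 states 186 per arm. An effect size of 0.4, 90% power and two-sided 0.05 need 133 per arm by the exact t-test. 133 × 1.2 / 0.86 = 185.6, rounded up to 186. This reproduces, and nothing below alters it.

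**3. Expected deaths.** Section 12.6.3 states "we assumed a dropout rate of 11% and a mortality rate at 12 weeks of 3" per cent. With 380 patients:

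- By 12 weeks: 0.03 × 380 = 11.4.
- By 6 months (26 weeks), assuming a constant hazard: 380 × (1 − 0.97^(26/12)) = 24.3. The document projects no 6-month figure.

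**4. Count outcome, equal follow-up.** If utilization is one abstracted total per patient, the mixed model reduces to ordinary linear regression. Gamma-Poisson counts were assumed, with mean 0.5 and dispersion 0.5 or 2. The ratio of model-based to true standard error was 0.986, 0.975, 1.013 and 1.008 over the settings tried. There is no material bias.

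**5. Count outcome, unequal follow-up.** Assume no true difference in event rate and 190 per arm. Loss hazards are h and 3h per week, set so that overall 12-week loss is the plan's 11%. Only the 11% comes from the document.

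- Solving (1 − e^(−12h))/2 + (1 − e^(−36h))/2 = 0.11 gives h = 0.00493, so losses are 5.7% and 16.3%.
- Mean observed time over 26 weeks is m = (1 − e^(−26h))/h = 24.40 weeks in one arm. Replacing h by 3h gives 21.59 weeks in the other.
- With a weekly rate r = 0.5/26, the expected counts are 0.469 and 0.415, a spurious difference of 0.054.
- The variance per patient is r·m + r²(1 + k)·M2 − (r·m)², where k is the dispersion and M2 = 2[(1 − e^(−26h))/h² − 26e^(−26h)/h] (3h for the second arm). The standard error is 0.0770 for k = 0.5 and 0.0963 for k = 2.
- With δ = difference/SE = 0.703 and 0.562, the false-positive rate Φ(−1.96 + δ) + Φ(−1.96 − δ) is 0.108 and 0.087.
- Doubling the mean count to 1.0 gives 0.147 and 0.100.

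In 1,500 simulated trials at mean 0.5, a negative binomial model with log observed time as offset gave 0.051 (k = 0.5) and 0.057 (k = 2). A linear comparison of the same data gave 0.100 and 0.089.

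**The case against.** The strongest reply is that Section 12.5 is a loosely worded list and Section 12.5.2 is the operative plan. There the mixed model is tied to repeated measures and the next sentence supplies survival methods. Mortality is the only listed outcome that is naturally time-to-event. This largely stands: for mortality the problem is drafting, not evidence that a linear mixed model is intended.

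It is also fair that counts and binary outcomes are not left without analysis, since Mann-Whitney, Fisher and chi-squared tests are planned. The gap is confined to the adjusted results. Blinding helps as well: "the principal investigator and analysis team are blinded to participant randomization", which limits result-driven choice of model. It does not make an unsuitable model suitable.

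Three stronger readings are tempting, and the documents do not support them.

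- **Inflated false-positive rate for mortality.** A reader might infer this from putting 0/1 death status into a mixed model. It needs the unlikely reading of 12.5, a random-intercept covariance that the plan never states, and a 6-month contrast from the mixed model, whereas 12.5.2 gives visit-specific comparisons to two-sample tests. For the effect averaged over visits, or with visit-specific variances, simulated rates were 0.047 to 0.055.
- **Conflict with Section 12.1.** That section says outcomes "will be evaluated at each individual time point as well as across the intervention period". A reader might think this excludes a survival analysis. It does not: Kaplan-Meier estimates can be read at each time point, and a hazard ratio summarises the period.
- **An unusable adjusted Cox model.** With arm plus five covariates there are 11.4 / 6 = 1.9 deaths per term at 12 weeks, which looks thin. Yet in simulation the arm standard error was 0.644 unadjusted and 0.645 with six parameters, and 8 of 300 six-parameter fits had a non-finite coefficient (none of 300 at 6 months). Failures became common only under assumed sparse race and education categories. Preferring the unadjusted estimate is a matter of taste here.

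**Conclusion.** The point holds as a minor one. Sections 12.5 and 12.5.2 should be reconciled so that mortality is plainly assigned to Kaplan-Meier/Cox, as is very probably intended. The hospitalization/ER count and yes/no outcomes have only a linear mixed model as their adjusted method, and better-suited models should replace it.

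The size is modest. With equal follow-up, a linear model for one total per patient behaves acceptably. The benefit of a count model with an offset shows when observed time differs by arm: under an assumed threefold difference in loss rate, the linear comparison's false-positive rate is about 9 to 15%, against about 5 to 6% for the count model in the simulated cases. That range rests on assumed event rates, dispersion and loss pattern. It would shrink if record abstraction covers all patients for the same period.

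The reading of the text is secure. Only secondary outcomes are affected; the primary analysis and the sample size are not.

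**What to change.** 1. In 12.5, remove mortality from the linear-mixed-model sentence. In 12.5.2, name it as the Kaplan-Meier/Cox outcome and state a censoring date. Set time zero at randomization, which fits the intent-to-treat rule in 12.5.1 that "all data from study patients in both intervention and control arms are used, regardless of the level of adherence to the study arm".
2. Limit the linear mixed model to the repeated scale scores: ESAS, PROMIS-29, FACIT-Sp-12 and ZBI-12.
3. Analyse hospitalizations/ER visits by negative binomial regression with log observed post-operative time as offset, counting exposure from surgery. Say how patients who never have surgery are handled: randomization precedes surgery, so they have no post-operative time and the offset is undefined for them. Report deaths by arm alongside.
4. Use logistic models, mixed if the outcome is repeated, for binary outcomes such as presence of advance care planning.

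The cost is a few sentences in 12.5 and 12.5.2 and a few more models to code, with no new data. The small downside is that these outcomes would be reported as rate ratios and odds ratios instead of mean differences.

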### 12.5.1 Analysis Population

Our study will use an intent-to-treat approach in which all data from study patients in both intervention and control arms are used, regardless of the level of adherence to the study arm.

### 12.5.2 Analysis Plan

Depending on the format of the variable, the effect of group assignment (intervention or control) on the secondary outcomes will be tested at each visit with two-sample t-test/Mann-Whitney test or Fisher's exact test/chi-squared test. The effect of intervention on secondary variables after accounting for various confounding variables will be determined using a linear mixed model that accounts for within-subject variations due to repeated measures. For end-point secondary outcomes, Kaplan-Meier method or Cox proportional hazards models will be used.

The overall level of statistical significance was set at  $p<0.05$ . For all models, the research team will identify possible confounding variables for model adjustment, including baseline attributes. Using peer-reviewed literature, the research team has identified confounding variables that models will be adjusted for. These covariates include patient gender, age, race, education, and health status.

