##### 10.1.2 Measurement Definition

The primary outcome variable of this project is patient quality of life, measured by the Functional Assessment of Chronic Illness Therapy—Palliative Care (FACIT-PaL) Subscale.

	Study design	Participants	Outcomes and Measurement Times
SA1 (months 1-36)	
Randomized controlled trial (n=420 patients; Approx. n = 304 family members); Outcomes measured at approximately: - enrollment - 1 week after surgery - 1 month after surgery - 3 months after surgery - 6 months after surgery
	
Patients
 
Family members/ Companions
	
(1) Quality of life - Functional Assessment of Chronic Illness – Palliative Care (FACIT-PaL)** Subscales: (i) Functional Assessment of Cancer Therapy (FACT-G) (ii) Trial Outcome Index (TOI)
 
(2) Demographics
 
(3) Edmonton Symptom Assessment Score (ESAS)*
 
(4) Functional Assessment of Chronic Illness Therapy – Spiritual Well-being (FACIT-Sp-12)*
 
(5) Mood symptoms including anxiety and depression subscales – PROMIS-29
 
(6) Health care utilization* (# of post-operative hospitalizations and/or emergency room visits)
 
(7) Presence of advance care planning*
 
(8) Prognostic understanding*
 
(9) Mortality*
 
(1) Demographics
 
(2) Zarit Caregiver Burden Scale (ZBI-12)*
 
(3) Mood symptoms including anxiety and depression subscales – PROMIS-29
 
(4) Functional Assessment of Chronic Illness Therapy – Spiritual Well-being (FACIT-Sp-12) family/companion measure*
 
(5) Prognostic understanding*

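### Section 12.5.2 calls 0.05 the overall significance level for the secondary analysis, but tests 5 to 13 outcomes, most at several visits, with no multiplicity control and no statement that the p-values are nominal.

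*Combined protocol and SAP*

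**What the plan says.** All references are to the combined protocol and SAP.

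- **Testing rule.** Section 12.5.2 says that "the effect of group assignment (intervention or control) on the secondary outcomes will be tested at each visit", by t-test/Mann-Whitney or Fisher/chi-squared. Section 12.1 gives the same rule for primary and secondary outcomes: differences "will be evaluated at each individual time point as well as across the intervention period".
- **Second analysis.** Section 12.5.2 continues: "The effect of intervention on secondary variables after accounting for various confounding variables will be determined using a linear mixed model". It adds: "For end-point secondary outcomes, Kaplan-Meier method or Cox proportional hazards models will be used".
- **Level.** "The overall level of statistical significance was set at" p<0.05 (12.5.2). The same sentence stands in 12.4.2 for the primary analysis.
- **Outcome list.** Section 12.5 names five: "Secondary outcomes include physical symptom assessment, mood symptoms (measured through a subscale of PROMIS-29), spiritual distress assessment, mortality, and assessment of caregiver burden". The text of 10.2.2 lists more, and its table adds advance care planning. Section 12.5 has "mood symptoms (measured through a subscale of PROMIS-29", a single subscale, whereas the table in 10.1.2 has "Mood symptoms including anxiety and depression subscales", which is two.
- **Schedule.** Section 10.2.4 puts secondary assessment at baseline and at 1 week, 1 month, 3 months and 6 months after surgery. The calendar in section 9 shows this schedule only for the questionnaires. Advance care planning is at pre-study and 6 months, medical abstraction is at off-study, and prognostic understanding has no row.

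Only the primary outcome has a named time point (12.4, three months). The document contains no multiplicity method, testing order or key secondary outcome, and does not label the secondary tests exploratory or nominal.

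**The concern.** An overall level normally means the error rate across a set of tests. Here the set is undefined, the number of outcomes differs between sections, and nothing links the tests. A reader of the results could take an isolated p<0.05 at one visit on one patient or caregiver scale as having met a 5% overall standard, when that standard was applied to each test alone. The rationale in 2.3 cites benefits on symptoms, spiritual distress and caregiver burden in other populations, so such a result could easily be read as confirmation.

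Unadjusted secondary testing is defensible when it is declared. The problem is that this plan does not declare it, and uses a word that points the other way.

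**Working it through.** **The plan's own use of alpha.** The 0.05 in 12.5.2 is set, not derived. The one derived figure that uses alpha is the sample size in 12.6.2. For effect size 0.4, 90% power and two-sided 0.05, a two-sample t-test needs 132.3, so 133 per arm. Then 133 × 1.20 / 0.86 = 185.6, so 186 per arm, as stated. It rests on one outcome at 12 weeks and does not involve the secondary tests.

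**Number of outcomes.**
- Section 12.5: 4 scales (symptoms, mood, spiritual distress, caregiver burden) + mortality = 5.
- Section 10.2.2 text: 7 patient + 5 caregiver = 12. One on each side is qualitative, leaving 6 + 4 = 10.
- Section 10.2.2 table: adds advance care planning = 11.
- Anxiety and depression counted separately for patients and caregivers: 11 + 2 = 13.

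**Number of tests**, over the four post-surgery visits and leaving out the mixed models:
- Narrowest: 4 scales × 4 visits + mortality = 17.
- Widest: 10 repeated outcomes × 4 visits = 40, plus one test each for utilization, advance care planning and mortality = 43. The ten are ESAS, FACIT-Sp-12, anxiety, depression and prognostic understanding in patients, and ZBI-12, anxiety, depression, FACIT-Sp-12 and prognostic understanding in caregivers. Testing prognostic understanding at four visits is an assumption taken from 10.2.4.

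**If tests are independent.** Chance of at least one two-sided p<0.05 with no true effect = 1 − 0.95^m; expected number = 0.05m.
- m = 17: 1 − 0.95^17 = 58.2%; expected 0.85.
- m = 43: 1 − 0.95^43 = 89.0%; expected 2.15.
- Between them, the calendar questionnaires alone (8 scales × 4 visits = 32): 80.6%.

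**If tests are correlated.** The documents give no correlations, so these are assumptions. I simulated 100,000 multivariate normal vectors per scenario, with equal correlation between outcomes, equal correlation between visits and the product across both. Single outcomes are independent of the rest. The patient–caregiver correlation is either zero or equal to that between other outcomes; each cell shows zero first, then equal. A false benefit is a result beyond 1.96 in the direction of the intervention.

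| Outcome / visit correlation | 17 tests, any p<0.05 | 17 tests, false benefit | 43 tests, any p<0.05 | 43 tests, false benefit |
|---|---|---|---|---|
| 0.3 / 0.5 | 51%, 49% | 28%, 26% | 82%, 80% | 53%, 48% |
| 0.5 / 0.6 | 46%, 43% | 25%, 22% | 74%, 69% | 45%, 39% |
| 0.7 / 0.7 | 39%, 34% | 21%, 18% | 63%, 54% | 37%, 29% |

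The mixed-model tests come on top of these figures.

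**After the fix.** With one test per outcome, 5 tests give 1 − 0.95^5 = 22.6% and 13 give 1 − 0.95^13 = 48.7% if independent; expected numbers are 0.25 and 0.65. The family-wise rate would still exceed 5%, but the plan would no longer suggest otherwise.

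**The case against.** The strongest reply is that overall need not mean family-wise. The same sentence stands in 12.4.2, no text promises control across outcomes, and it may mean only that 0.05 is the threshold used throughout. That reading is fair. On it the 0.05 is a real per-test level, and a reader who inferred that the stated level does not exist would go too far. It does not remove the need for an edit, because the word then misdescribes a nominal level.

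Three other stronger readings are tempting, and the documents do not support them.

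- **That some 13 outcomes are tested at every visit.** Thirteen is the upper count, and 12.5 names five. End-point outcomes go to Kaplan-Meier or Cox models, and the calendar does not schedule advance care planning, utilization or mortality by visit. Hence 43 tests at most by this count, not 13 × 4 = 52.
- **That a false benefit is more likely than not.** The 58% and 89% are two-sided and count apparent harms as well. In the correlated scenarios a false benefit exceeds one half only for the widest count with the weakest correlations and unrelated patient and caregiver scales.
- **That the trial's conclusion could rest on a secondary result.** One primary outcome and time point are named (12.4), power rests on it (12.6.2), and 12.7 ties the superiority aim to it. No text lets a secondary outcome carry the conclusion.

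**Conclusion.** The point holds in a limited form. Section 12.5.2 describes 0.05 as overall for a secondary analysis that has no defined family, no priority time point and no control. As an overall level it is missed on every count: 58% (independent) or about 34–51% (correlated) for 17 tests, and 89% or about 54–82% for 43. The correlated ranges rest on assumed correlations of 0.3–0.7 between outcomes and 0.5–0.7 between visits, patient–caregiver correlation from zero to equal, and independent single outcomes. Stronger correlation would lower them. The chance of a false result favouring the intervention is about 18–28% and 29–53% on the same assumptions.

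If a per-test threshold was meant, the defect is one misleading word and a missing statement. Either way the text should change. This is a matter of how secondary results are labelled and read; the primary outcome and the 186 per arm stand.

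**What to change.** In 12.5.2:

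1. Delete the word overall. State that 0.05 is per test and unadjusted, so secondary results are nominal.
2. Name 3 months, matching the primary, as the single tested comparison for each repeated secondary outcome, and say which analysis supplies it (the per-visit test or the mixed model).
3. Report the other visits as estimates with 95% confidence intervals, without significance claims.
4. Give one list of secondary outcomes that agrees with 10.2.2, and settle whether PROMIS-29 mood is one subscale or two. The same edit can reconcile mortality, which 12.5 places under the linear mixed model and 12.5.2 would treat as an end-point outcome.

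The cost is SAP wording only, with no new data or patients. The downside is fewer nominally significant secondary results.

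A Holm procedure is optional and needed only if the sponsor wants a confirmatory secondary claim. On the widest list the families would be 8 patient and 5 caregiver comparisons. The first patient step would be 0.05/8 = 0.00625. At effect size 0.4 and 186 × 0.86 / 1.20 = 133.3 effective patients per arm, power at that step would be Φ(0.4 × √(133.3/2) − 2.73) = Φ(0.53), about 70%, against 90.4% at 0.05.
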